**Table 1. Diagnosis codes for inclusion criteria.**

KCD-6 	KCD-7 
I48 (Atrial fibrillation and flutter)	I48 (Atrial fibrillation and flutter)
I480 (Atrial fibrillation)	I480 (Paroxysmal atrial fibrillation)
I481 (Atrial flutter)	I481 (Persistent atrial fibrillation)
	I482 (Chronic atrial fibrillation)
	I483 (Typical atrial flutter)
	I484 (Atypical atrial flutter)
	I489 (Atrial fibrillation and atrial flutter, unspecified)

KCD-6, Korean version of ICD-10 (6th revision); KCD-7, Korean version of ICD-10 (7th revision)

1) KCD-6 diagnosis codes will be used from 1 July 2015 to 31 December 2015.

2) KCD-7 diagnosis codes will be used from 1 January 2016 to 30 November 2016.

[NOTE] KCD code is based on ICD-10 and almost similar, but KCD code is slightly different from ICD-10 (e.g., ICD-10 is more subdivided and extensive than KCD code).

3. Patients prescribed aspirin, warfarin, or NOACs during intake period (from July 1, 2015 to November 30, 2016)

*[Note] NOACs include apixaban, dabigatran, and rivaroxaban.*

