### 8.2.2 Exclusion criteria

Patients meeting any of the following criteria will not be included in the study.

1. Medical claims indicating diagnosis or procedure for hip/knee replacement surgery within 6 weeks prior to index date
2. Medical claims indicating a diagnosis code indicative of rheumatic mitral valvular heart disease, mitral valve stenosis during the 12-month baseline period  
(Valvular AF / Prosthetic heart valves)
3. Medical claims indicating a diagnosis code of VTE (Venous thromboembolism) during the 12-month baseline period
4. Medical claims indicating a diagnosis or procedure code of transient AF, or cardiac surgery during the 12-month baseline period

(Thyrotoxicosis, Hypertrophic cardiomyopathy, Elective defibrillation, radiofrequency ablation, or left atrial appendage occlusion)

5. Medical claims indicating a diagnosis code of other conditions during the 12-month baseline period  
(End-stage chronic kidney disease / Kidney transplant / Dialysis / Pericarditis)
6. For the comparison of “NOAC versus NOAC”, and “NOAC versus warfarin”, patients with any OACs (apixaban, dabigatran, rivaroxaban, or warfarin) in the pre-index period (from 1 year prior to the day before index date)
  - *[NOTE] Patients prescribed antiplatelets in the pre-index period will not be excluded.*
7. For the comparison of “NOAC versus aspirin”, patients with following medications in the pre-index period (from 1 year prior to the day before index date)
  - NOAC user: OACs (apixaban, dabigatran, rivaroxaban, warfarin)
  - Aspirin user: none
  - *[NOTE] NOAC user is defined as OAC naïve user and aspirin user is allowed to have OACs or antiplatelets in the pre-index period.*

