Exclusion criteria	Exclusion criteria	HIRA database	
Claims with the following KCD codes or procedure codes:
 
 
1. Valvular AF/ Prosthetic heart valves: I05, I08, I09, I34, Q23, T820, T826, Z952, Z953, Z954            - Korean procedure codes: M6580, M6581, M6582, O1791, O1792, O1793, O1794, O1795, O1796, O1797, O1798, O1799, M6531, M6532, M6533, O1690, O1730, 1740, O1750, O1760, O1770, O1781, O1782, O1783, O1810, O1826
 
2. End-stage of chronic kidney disease/dialysis: N185, T824, Y602, Y612, Y622, Y841, Z49, Z992, E1022, E1122, E1222, E1322, E1422
 
3. Kidney transplant: Z940
 
4. Venous thromboembolism: I636, I676, I801, I802, I803, I808, I809, I81, I822, I823, I829, I26
 
5. Hip or knee replacement            - Korean procedure codes: N0711, N0715, N1711, N1715, N1721, N1725, N2070, N2072, N2077, N2710, N2712, N2717, N3710, N3712, N3717, N3720, N3722, N3727, N4710, N4712, N4717, N4720, N4722, N4727
 
6. Thyrotoxicosis: E05
 
7. Pericarditis: I30, I31, I32
 
8. Hypertrophic cardiomyopathy: I422
 
9. Elective defibrillation, radiofrequency ablation, or left atrial appendage occlusion            - Korean procedure codes: M5880, M6540, M6542, M6545, M6547, M6511
 

Follow-up period	Follow-up period	HIRA database	
From the index date until the first occurrence of the following whichever came first:
 
 
1. Discontinuation: maximum of a 30-day gap after the calculated time to finishing the pack based on pack size and number of tablets per day. Switching: switch to any other study drugs
 
2. Outcome occurrence
 
3. Study ends: November 30, 2016
 

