Diabetes with chronic complication	E10.2-E10.5, E10.7, E11.2-E11.5, E11.7, E12.2-E12.5, E12.7, E13.2-E13.5, E13.7, E14.2-E14.5, E14.7	2
Hemiplegia or paraplegia	G04.1, G11.4, G80.1, G80.2, G81.x, G82.x, G83.0-G83.4, G83.9	2
Any malignancy, including leukemia and lymphoma	C00.x-C26.x, C30.x-C34.x, C37.x-C41.x, C43.x, C45.x-C58.x, C60.x-C76.x, C81.x-C85.x, C88.x, C90.x-C97.x,	2
Renal disease	I12.0, I13.1, N03.2-N03.7, N05.2-N05.7, N18.x, N19.x, N25.0, Z49.0-Z49.2, Z94.0, Z99.2	2
Moderate or severe liver disease	I85.0, I85.9, I86.4, I98.2, K70.4, K71.1, K72.1, K72.9, K76.5, K76.6, K76.7	3
AIDS/HIV	B20.x-B22.x, B24.x	6
Metastatic solid tumor	C77.x-C80.x	6

Table 12. Baseline Medications

Class	Drug
NSAIDs	Bromfenac, Celecoxib, Diclofenac, Etodolac, Fenoprofen, Flurbiprofen, Ibuprofen, Indomethacin, Ketoprofen, Ketorolac, Naproxen, Meclofenamate, Mefenamic acid, Meloxicam, Nabumetone, Oxaprozin, Piroxicam, Sulindac, Tolmetin
Antiplatelets	Aspirin, Clopidogrel, Prasugrel, Ticlopidine, Cilostazol, Abciximab, Tirofiban, Dipyridamole, Ticagrelor
PPI	Omeprazole, Pantoprazole, Lansoprazole, Rabeprazole, Esomeprazole, Dexlansoprazole
H ₂ -receptor antagonists	Cimetidine, Ranitidine, Famotidine, Nizatidine, Roxatidine, Lafutidine
Antiarrhythmics	Quinidine, Procainamide, Mexiletine, Propafenone, Flecainide, Amiodarone, Bretylium, Dronedarone, Propranolol, Atenolol, Esmolol, Verapamil, Diltiazem, Sotalol
Digoxin	Digoxin
Statins	Atorvastatin, Fluvastatin, Lovastatin, Pitavastatin, Pravastatin, Roxuvastatin, Simvastatin

Table 13. Exclusion Criteria

Condition	KCD Code or Korean Procedure Codes
Valvular AF/ prosthetic heart valves	I05, I08, I09, I34, Q23, T820, T826, Z952, Z953, Z954 - Korean Procedure Codes: M6580, M6581, M6582, O1791, O1792, O1793, O1794, O1795, O1796, O1797, O1798, O1799, M6531, M6532, M6533, O1690, O1730, 1740, O1750, O1760, O1770, O1781, O1782, O1783, O1810, O1826
End-stage of chronic kidney disease/ dialysis/ kidney transplant	N185, T824, Y602, Y612, Y622, Y841, Z49, Z992, E1022, E1122, E1222, E1322, E1422, Z940
Venous thromboembolism	I636, I676, I801, I802, I803, I808, I809, I81, I822, I823, I829, I26
Thyrotoxicosis	E05
Pericarditis	I30, I31, I32
Hypertrophic	I422

NIS Protocol <X9001134>
Statistical Analysis Plan
<Version 3.0> <03 May 2018>

Condition	KCD Code or Korean Procedure Codes
cardiomyopathy	

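### Hypertrophic cardiomyopathy is excluded without a subtype limit but coded only as I422, so patients coded I421 stay in; the venous thromboembolism row may have a similar, less certain gap at I828.

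*Protocol*

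**What the plan says.** Criterion 4 in Protocol 8.2.2, repeated in SAP 3.1, covers transient AF and cardiac surgery in the 12-month baseline. It spells these out as "Thyrotoxicosis, Hypertrophic cardiomyopathy, Elective defibrillation, radiofrequency ablation, or left atrial appendage occlusion". Nothing restricts the cardiomyopathy to one form. The operational definition in Protocol 8.3, exclusion row 8, is "Hypertrophic cardiomyopathy: I422", and SAP Appendix 2, Table 13 gives the same single code.

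Criterion 3 is equally general: "Medical claims indicating a diagnosis code of VTE (Venous thromboembolism) during the 12-month baseline period". Its code row in Protocol 8.3 is "Venous thromboembolism: I636, I676, I801, I802, I803, I808, I809, I81, I822, I823, I829, I26", and SAP Table 13 has the same twelve codes.

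On the coding system, the note to Protocol Table 1 says "KCD code is based on ICD-10 and almost similar, but KCD code is slightly different from ICD-10", and adds that ICD-10 is the more finely divided of the two.

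**The concern.** The criterion names a disease and the code row names one code of it. If hypertrophic cardiomyopathy is split over two codes, the row removes one form and leaves the other, so the analysed cohort is not the one described in 8.2.2. The two documents agree with each other, so neither repairs the gap, and neither gives a reason for the narrower list. The VTE row raises the same question in milder form: it includes the unspecified code from I82 but not the code for other specified veins. At stake is whether the written rules deliver the stated population. Alpha, power and the stated study size are not affected.

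**Working it through.** **Inputs.** The exclusion code rows come from Protocol 8.3 and SAP Table 13, the criteria from Protocol 8.2.2, and the anticipated size of about 150,000 from Protocol 8.5. The plan states no figure on this point that could be reproduced.

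**Step 1: does any listed code cover the missing ones?** Each queried code was compared by prefix with every diagnosis code in the exclusion rows.

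| Code | Matched by an exclusion row? |
|---|---|
| I422 | yes (I422) |
| I421 | no |
| I808, I809 | yes (each listed) |
| I829 | yes (I829) |
| I828 | no |
| I820, I821 | no |

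Neither I42 nor I82 is listed as a parent code. Other rows do use whole categories: E05 for thyrotoxicosis, and I30, I31 and I32 for pericarditis.

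**Step 2: is I42 subdivided in the coding used here?** Yes, on the documents' own evidence. The exclusion row uses I422, and the Charlson heart-failure row in SAP Table 11 uses I42.0 and I42.5-I42.9. The documents print no label for I421. Its meaning (obstructive hypertrophic cardiomyopathy) is the ICD-10 definition and has to be confirmed for KCD. The same holds for I828 (embolism and thrombosis of other specified veins).

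**Step 3: is the VTE row consistent?** From I80 it takes both the other-sites code and the unspecified code (I808, I809). From I82 it takes I829 but not I828. It also leaves out I800, I820 and I821, and it adds I636, I676 and I81 from outside those two categories. That pattern fits either an oversight or a choice of sites.

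**Step 4: scale.** The documents give no counts, so every share below is an assumption. Number retained = N × prevalence × share carrying only the missing code, with N = 150,000.

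- I421, assuming prevalence 0.2%-1% and share 10%-50%: 150,000 × 0.002 × 0.10 = 30; 150,000 × 0.01 × 0.50 = 750.
- I828, assuming prevalence 0.5%-2% and share 2%-10%: 150,000 × 0.005 × 0.02 = 15; 150,000 × 0.02 × 0.10 = 300.
- Sum: 30 + 15 = 45 to 750 + 300 = 1,050, or 0.03% to 0.7% of 150,000.

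The base of 150,000 is the count before exclusions, so numbers in the matched sub-datasets would be lower. A patient with any other listed exclusion code in the applicable look-back is removed anyway.

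**The case against.** The strongest objection is that the documents never label I421 or I828, and that the Table 1 note warns that KCD is not identical to ICD-10. This stands as a reason to check the code books before editing. It does not remove the point about I421: a code label is a classification definition, the documents themselves subdivide I42, and nothing in criterion 4 suggests that only the non-obstructive form was meant.

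For I828 the objection carries more weight. I800, I820 and I821 are absent too, so the row may be a deliberate list of sites, possibly taken from the harmonized protocol that the amendment log mentions. Hence this half is a query, not an error.

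Three stronger readings are tempting, and the documents do not support them.

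- A reader might infer that retained VTE patients collect in the NOAC and warfarin arms, because VTE is itself a reason to anticoagulate. Exclusions 6 and 7 cut across this. A patient given a study anticoagulant in the year before index is already out of those arms but may remain in the aspirin arm, while one first anticoagulated at index may enter a NOAC or warfarin arm. The net direction is unknown, and six of the nine sub-datasets have no aspirin arm.
- A reader might infer that the planned adjustment cannot balance these diseases, since the risk scores do not include the codes. SAP 5.1 also allows comorbidities in the propensity model and leaves the final covariate list open.
- A reader might apply a single share, such as 0.2%-1% of 150,000 (300 to 1,500), as if it measured the problem. No such share is in the documents.

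**Conclusion.** The point on hypertrophic cardiomyopathy holds: as coded, the rule misses part of the disease that criterion 4 names, provided KCD keeps the ICD-10 meaning of I421. The point on I828 is weaker and turns on whether the omission was intended. The number affected is unknown; tens to about a thousand of roughly 150,000 is only an illustration under the assumed shares. The effect on any hazard ratio is probably small, with no direction that can be stated. This is a minor correction worth making because it is cheap.

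**What to change.** 1. Look up I421 and I828 in the KCD-6 and KCD-7 code books.
2. If I421 is confirmed, change the hypertrophic cardiomyopathy row to I421, I422 in Protocol 8.3 and SAP Table 13 together. If only the non-obstructive form was meant, say so in criterion 4 instead.
3. For the VTE row, state whether the choice of I80 and I82 codes is deliberate. If it is not, add I828 in both documents.
4. Report the number of patients removed by each exclusion row, so that the size of the change is visible.

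The cost is one or two codes in one table of each document, a rerun of cohort selection if it has already been done, and slightly fewer patients. The sponsor logged the previous addition of codes to Table 13 as a substantial SAP amendment, so the same route would presumably apply.

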#### ***Secondary objectives***

1. To explore and understand more detailed drug utilization patterns
  - o Standard doses versus reduced doses of NOACs

- Patterns of usage (i.e., switching, discontinuation) and clinical events preceding the pattern
- Compliance (i.e., medication possession ratio)

2. To compare effectiveness and safety of antithrombotic therapies versus not using therapies among low risk patients (low score of CHA2DS2-VASc)

**Study design:** Retrospective cohort study

**Population:** Subjects with atrial fibrillation diagnosed (from January 1, 2007 up to and including the index date\*) who newly initiated antithrombotic therapies (NOACs (not including edoxaban), warfarin, or used aspirin) between July 1, 2015 and November 30, 2016 in the Korean Health Insurance Review & Assessment Service (HIRA) database

*\*Index date is the first prescription date of study drugs, including NOACs, warfarin, and aspirin during the intake period (from July 1, 2015 to November 30, 2016).*

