**Figure 1. Study design scheme**

## 8.2 Setting

### 8.2.1 Inclusion criteria

Patients must meet all of the following inclusion criteria to be eligible for inclusion in the study:

1. Patients aged 18 years or older on the index date
2. Patients had  $\geq 1$  medical claim for AF (refer to Table 1) before or on the index date with at least one hospitalization or at least two outpatient visits:

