### 8.3 Variables

Variable	Role	Data source(s)	Operational definition
Composite of hemorrhagic stroke, ischemic stroke and systemic embolism	Primary effectiveness outcome	HIRA database	
Claims with the following KCD codes in all diagnosis codes (main and sub-diagnosis codes) whichever came first (i.e., the first occurred event will be used):
 

1. Ischemic stroke: G459, I63, I693

2. Systemic embolism: I74

3. Hemorrhagic stroke: I60, I61, I62, I690, I691, I692

 
[NOTE] Hospitalization and CT or MRI codes (brain CT or MRI for ischemic stroke and hemorrhagic stroke; any CT or MRI for systemic embolism) were also required for identification.
 
*Brain CT or MRI:
 
CT: HA441, HA451, HA461, HA471, HA851
 
MRI: HE101, HE102, HE135, HE201,

Variable	Role	Data source(s)	Operational definition

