## 8.4 Data sources

South Korea has a universal health coverage system that the National Health Insurance covers approximately 97% of the overall South Korean population. The claims data of Health Insurance Review & Assessment Service (HIRA) contains 46 million patients per year that account for 90% of the total population in Korea and include claims from almost 80,000 healthcare service providers across South Korea as of 2011.

The claims data of HIRA includes patients' diagnosis, treatment, procedures, surgical history, and prescription drugs which provide a valuable resource for healthcare service research. Data elements captured in the HIRA database include patient-level demographic and plan enrollment information (e.g., start and stop dates of health plan enrollment), date-stamped (month and year) inpatient and outpatient medical claims (e.g., diagnosis codes, procedure codes, provider specialty), and pharmacy claims (e.g., prescription fill/refill dates, drug name/code, dosage). While procedure codes that identify patient receipt of laboratory tests are available, actual laboratory values and test results are not available.

The HIRA database has unique attributes that make it a useful data source for this study. The key advantage of the HIRA database relative to other potential data sources (e.g., medical chart review) is that it is a population level data including most of Korean population and it will provide a large analytic sample and provide accurate claim-level treatments pattern and health care utilization across all provider settings (e.g., inpatient, outpatient, pharmacy) in patients' spectrum of care.

One key limitation of the HIRA database is that it does not include clinical variables such as laboratory values and clinical markers. To overcome this limitation, the Charlson comorbidity index and overall healthcare utilization observed during the pre-index period will be used as proxy measures to incorporate the overall health status of the individual patients.

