4 ENDPOINTS AND COVARIATES

4.1 EFFICACY/ EFFECTIVENESS ENDPOINT(S)

Table 1. Effectiveness Endpoints

Variable	Role	Operational definition
Stroke/Systemic embolism	Primary effectiveness outcome	Hemorrhagic stroke, ischemic stroke and systemic embolism requiring hospitalization will be identified using hospital claims which had a hemorrhagic stroke, ischemic stroke or systemic embolism code whichever came first (i.e., the first occurred event will be used). All KCD diagnosis codes (main and sub-diagnosis codes) will be used. Especially, hospitalization and brain CT or MRI codes will be needed to identify ischemic stroke and hemorrhagic stroke. For systemic embolism, hospitalization and any CT or MRI codes will be used (Appendix 2, Table 7).
Individual outcome of primary outcome	Secondary effectiveness outcome	Individual outcome of hemorrhagic stroke (diagnosis codes in all main and sub-diagnosis codes + hospitalization + brain CT or MRI), ischemic stroke (diagnosis codes in all main and sub-diagnosis codes + hospitalization + brain CT or MRI), and systemic embolism (diagnosis codes

Variable	Role	Operational definition
		in all main and sub-diagnosis codes + hospitalization + any CT or MRI)

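### Outcome follow-up opens on the index date with no rule that the outcome admission must start later, so a stroke or bleed that preceded the prescription can be counted as on-treatment

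*Protocol*

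**What the plan says.** Protocol 8.3 sets the follow-up period as "From the index date until the first occurrence of the following whichever came first": discontinuation or switching, an outcome, or study end. The Abstract (Population) fixes time zero: "Index date is the first prescription date of study drugs, including NOACs, warfarin, and aspirin during the intake period". The look-back for prior drug use (Protocol 8.2.2, criteria 6 and 7) covers the period "from 1 year prior to the day before index date", so the index day is not part of that look-back and belongs to follow-up.

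AF may be established "before or on the index date with at least one hospitalization or at least two outpatient visits" (Protocol 8.2.1), so a single admission that includes the index day can qualify a patient.

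An outcome is a hospital claim with a listed code in any diagnosis position, with imaging required for stroke, systemic embolism and intracranial hemorrhage. The first such event is the one used (Protocol 8.3; SAP 4.1 and 4.2). SAP 3.1 states when follow-up ends but not when it starts.

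On date precision, Protocol 8.4 and SAP 2.1 both describe "date-stamped (month and year) inpatient and outpatient medical claims", whereas pharmacy claims are said to carry fill and refill dates.

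**The concern.** Consider a patient admitted with an acute stroke, imaged, found to have AF, and given a first anticoagulant prescription on the day of admission. That one admission supplies the AF diagnosis, the index date and the first outcome. The stroke is a reason for treatment, yet it enters the analysis as a result of treatment. Because an outcome ends follow-up, the patient's real time at risk for that outcome is lost too.

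Propensity scores do not cure this. They balance prior stroke and bleeding as covariates, but they do not stop a pre-drug event from being counted as an outcome. SAP 4.3 (Table 3) itself lists stroke, systemic embolism and major bleeding as events after which a physician might change anticoagulants, so the link between event and prescription is foreseen in the plan. Both primary outcomes are exposed.

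**Working it through.** **Step 1: is there a safeguard?** I looked for a later start of follow-up, a blanking window, a condition on the admission date, or an exclusion for recent stroke or bleeding. I checked the exclusion criteria (Protocol 8.2.2 and 8.3; SAP 3.1), the endpoint tables (SAP 4.1, 4.2), the one sensitivity analysis (multinomial IPTW, SAP 5.1) and the limitations (Protocol 8.9). None contains such a rule. Figure 1 was not readable in the text available to me.

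**Step 2: which admissions fall inside follow-up as written?**

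| Admission | Event date used | Inside follow-up? |
|---|---|---|
| Starts before the index day | Admission start | No |
| Starts before the index day and contains the prescription | Discharge, or an imaging or claim date on or after the index day | Yes |
| Starts on the index day | Any of the four | Yes |
| Earlier in the index month | Month and year only | Cannot be ordered, so can be counted |

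Row 3 needs no assumption about the date field. Row 2 turns on a choice that the documents do not make. Row 4 applies only if the month-and-year description is literal.

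**Step 3: is it literal?** Other rules need finer dates: joint replacement within 6 weeks before index, and AF recorded before or on the index date. The sentence is also doubtful in another respect. It lists plan enrollment start and stop dates, while Protocol 8.9.3 says the database has no eligibility data. The passages must be reconciled.

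**Step 4: possible size.** The plan has no figure to reproduce: its study size is a count of AF patients, with no event rate or power calculation. For illustration:

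apparent ratio = (HR × r × T + q1) / (r × T + q0)

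- r, true on-treatment event rate: 2 to 5 per 100 person-years (assumed).
- T, mean follow-up: 0.25 to 0.71 years (assumed). The upper end comes from the study window: 1 July 2015 to 30 November 2016 is 518 days, and 518 / 2 / 365.25 = 0.71 with uniform entry and no discontinuation.
- q1, q0: share of patients in each arm with a pre-drug event counted as an outcome (assumed).

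Middle case, r = 0.03 and T = 0.5, so rT = 0.015:

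- q1 = 1%, q0 = 0.5%, true HR 1.00: 0.025 / 0.020 = 1.25.
- q1 = q0 = 2%, true HR 0.70: (0.0105 + 0.02) / 0.035 = 0.87.

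Over the whole grid of r and T:

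| q1, q0 | True HR | Apparent ratio |
|---|---|---|
| 1%, 0.5% | 1.00 | 1.12 to 1.50 |
| 1%, 0.5% | 0.70 | 0.86 to 1.35 |
| 3%, 1% | 1.00 | 1.44 to 2.33 |
| 2%, 2% | 0.70 | 0.81 to 0.94 |

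Half of an arm's counted events are spurious when q equals that arm's true event proportion. In an arm with true rate r this is rT, which runs from 0.02 × 0.25 = 0.5% to 0.05 × 0.71 = 3.55%. With q1 = q0 = 0 the apparent ratio returns to the true HR.

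**Step 5: month-only dating, background events alone.** On average (365.25 / 12 − 1) / 2 = 14.7 days before the index date share its calendar month. At a constant background rate this adds 14.7 / 365.25 / T spurious events relative to true ones: 6% at T = 0.71, 8% at 0.5 and 16% at 0.25. Events that prompted the prescription would come on top.

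**The case against.** The strongest reply is that this is an unstated detail. If the program dates an event at admission and uses day-level dates, a stay that began before the prescription falls outside follow-up on Protocol 8.3's own wording. Only admissions starting on the index day remain. That is right, and it narrows the problem. It does not remove it, because the index day is inside follow-up by the plan's own rule and the date field is nowhere named.

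Three stronger readings are tempting, and the documents do not support them.

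- **That every stroke or bleed leading to a prescription is counted.** This depends on the date field. The supported statement is that such events can be counted.
- **That month-only dating is established.** The sentence describes the database; it is not an analysis rule, and it conflicts with rules that need day-level ordering.
- **That all hazard ratios are biased differentially.** The contrast between OAC-naive starters and aspirin users with no new-user restriction exists only in sub-datasets 7 to 9. In sub-datasets 1 to 6 both arms are OAC-naive starters, and criterion 6 removes OAC-to-OAC changes. Equal contamination there pulls a true effect toward the null. Differential bias would need post-event prescribing to favour one drug, which is possible but not shown.

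Figure 1 might show a later start of follow-up. If so, the text should say it too.

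**Conclusion.** The point stands in this form. As written, an outcome admission starting on the index day is counted as on-treatment. One that contains the index prescription can be, depending on an unnamed date field. Events earlier in the index month can also be counted, but only if medical claims truly lack day-level dates. Both primary outcomes are affected.

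The size is unknown. The ranges above rest on assumed rates, follow-up and contamination shares, and the documents supply none of these shares. With day-level dates and events dated at admission, the share would be limited to same-day admissions and could lie below the values tabulated. The illustration shows why the gap still matters: follow-up is at most 518 days, true events per patient are few, and a share of one or two percent can be as large as the true event proportion.

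Differential bias is most plausible in NOAC versus aspirin. Its direction is not fixed by the documents. A stroke that prompts a first anticoagulant would load events onto the NOAC arm. A bleed that moves a prior anticoagulant user to aspirin, which criterion 7 allows, would load them onto the aspirin arm.

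**What to change.** In Protocol 8.3 and SAP 3.1, 4.1 and 4.2:

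1. Start outcome follow-up on the day after the index date.
2. Name the admission start date as the event date.
3. Count an outcome only if that date is later than the index date, in every arm and for both primary outcomes. Treat admissions that contain or precede the index date as baseline history.
4. Reconcile the month-and-year description in Protocol 8.4 and SAP 2.1 with the 6-week and AF-timing rules, and state the date precision actually available.
5. Only if day-level dates are truly unavailable, exclude index-month events and start time at risk on the first day of the next month.

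The cost of items 1 to 4 is wording, one date condition in the program, and the loss of true index-day events. The fallback in item 5 costs more. It drops about 15 days per patient on average (about 8% of a 0.5-year follow-up, 16% of 0.25 years), plus patients who have an event or discontinue before the next month begins. For that reason it should not be the default.
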